7.4. End-of-Treatment Visit

Patients completing all 5 cycles should undergo the following assessments at the end (\pm 1 week) of the last cycle:

- Complete physical examination (including vital signs)
- Ophthalmologic examination by an ophthalmologist
- ECHO or MUGA scan
- 12-Lead ECG
- Complete blood count (including differential count) and biochemistry
- Urinalysis
- Coagulation profile
- Performance status
- Tumor evaluation will be done (using MRI [magnetic resonance imaging] and/or CT scan and/or ¹²³I-MIBG scan and/or ¹⁸F-FDG-PET and/or bone marrow assessment)

Patients who discontinue study intervention early (receiving < 5 cycles) should also undergo EOT assessments, if clinically reasonable.

The EOT Visit is to be conducted ≤ 7 days after the investigator determined that the patient must permanently discontinue study drug. If routine laboratory tests (eg, hematology, clinical chemistry) were completed ≤ 7 days before the EOT Visit, these tests do not need to be repeated. A tumor assessment is not required at the EOT Visit if ≤ 6 weeks have passed since the last assessment. If EOT Visit did not occur until the planned Safety Follow-up Visit, then it can be used as replacement for the Safety Follow-up Visit.

Post-study treatment is allowed after the EOT Visit, at the discretion of the investigator, according to the treatment guideline and the local practice.

See Section 7.4 for assessments to be performed for the EOT Visit.

See Section 7.5.1 for details on the Safety Follow-up Visit.

7.5. Follow-up Periods

7.5.1. Safety Follow-up Period

Patients who permanently discontinue study drug will be asked to return to the clinic for the Safety Follow-up Visit, which is required to be conducted within 40 days [\pm 7 days] after the last dose of study drug or before the initiation of new anticancer therapy, whichever occurs first.

All AEs, including serious adverse events (SAEs), will be collected as described in Section 9.5.

See Appendix 1 for assessments to be performed at the Safety Follow-up Visit.

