7.6.2. Patient Discontinuation From the Study (End of Study for an Individual Patient)

Patients may discontinue from the study for reasons that include but are not limited to the following:

- Patient withdrawal of consent
- Death
- Lost to follow-up
- Completion of all study assessments

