9.5. Timing, Frequency, and Method of Capturing Adverse Events and Serious Adverse Events

9.5.1. Adverse Event Recording Period

After informed consent has been signed but before the administration of the study drug(s), only SAEs should be reported.

After the first dose of study drug(s), all AEs and SAEs, regardless of relationship to study drug, will be reported until 40 days after last dose of study drug. All SAEs considered related to the study drug(s) that are brought to the attention of the investigator should be reported regardless of time since the last dose of treatment.

AEs and SAEs should be recorded according to the details in Table 5. For the follow-up period for AEs, see Section 9.2.4. For the definition of treatment-emergent adverse events (TEAEs), see Section 10.2.2.

Table 5: Guidance for Duration of Recording New or Worsening Adverse Events

Event Type	Record new or worsening events that occur during this period								
Event Type	Begin	End							
SAEs ^a	Signing of informed consent	Up to 40 days after last dose of study drug; initiation of new anticancer therapy, death, withdrawal of consent, or loss to follow-up, whichever comes first							
All nonserious AEs	First dose of study drug	Up to 40 days after last dose of study drug; initiation of new anticancer therapy, death, withdrawal of consent, or loss to follow-up, whichever comes first							

Abbreviations: AE, adverse event; SAE, serious adverse event.

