10.1.5. Prior and Concomitant Medications

Prior medications will be defined as medications that stopped before the day of first dose of study drug(s). Concomitant medications will be defined as medications that 1) started before the first dose of study drug(s) and were continuing at the time of the first dose of study drug(s), or 2) started on or after the date of the first dose of study drug(s) up to 40 days after the patient's last dose (as of the Safety Follow-up Visit). Concomitant medications will be coded using the World Health Organization Drug Dictionary drug codes and will be further coded to the appropriate Anatomical Therapeutic Chemical code indicating therapeutic classification. Prior and concomitant medications will be summarized and listed by drug and drug class. A listing of prior and concomitant medications will be provided.

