- b The EOT Visit is conducted within ± 1 week of the end of Cycle 5. For early termination, the EOT Visit is conducted ≤ 7 days after the investigator determines that the patient must permanently discontinue the study drug or the patient decides to withdraw from the study before the end of Cycle 5.
- ^c Safety Follow-up Visit: within 40 days [± 7 days] after last dose of study drug; initiation of new anticancer therapy, death, withdrawal of consent, or loss to follow-up, whichever comes first.
- ^d Pregnancy test in WOCBP is described in Appendix 4.
- ^e If HCV-Ab positive, HCV-RNA test will be required for eligibility check.
- f Physical examinations is presented in Section 8.2.2.
- g At each timepoint, 3 consecutive 12-lead ECGs should be performed approximately 2 minutes apart to determine the mean QTcF interval.
- h Chest X-ray should be performed within 7 days before the start of dinutuximab beta infusion in each cycle. It can be skipped if chest MRI or CT scan has been performed already before administration per investigator's discretion.
- if clinical chemistry, hematology, coagulation and urinalysis at screening are not performed ≤ 7 days before study drug administration on Day 1 of Cycle 1, these tests should be repeated and reviewed before study drug administration. After Day 1 of Cycle 1, results are to be reviewed within 72 hours before study drug administration (Section 8.2.5).
- ^j The test for clinical chemistry, hematology, coagulation, and urinalysis, excluding PK sampling, will be performed within 72 hours before study drug administration on Day 1 of each cycle. All laboratory tests with values considered clinically abnormal during participation in the study or within 40 days after the last dose of study drug should be repeated until the values return to normal or baseline or are no longer considered clinically significant by the investigator or medical monitor (Section 8.2.5).
- k The recommended dose of dinutuximab beta depends on the patient's body surface area (BSA) and the actual dose is calculated on every Day 1 of Cycle 1 to 5 (BSA = SQRT [weight (kg) x height (cm)/ 3600]).
- ¹PK sampling time refers to Table 4 provided in Section 8.3.
- ^m PK sampling on Day 15 and Day 22 in Cycle 1 is optional.

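### The Safety Follow-up Visit may fall up to 7 days before the 40-day adverse event window closes, leaving those days without a scheduled contact

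*Protocol*

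**What the plan says.** **Timing of the visit.** Protocol 7.5.1 has patients who permanently stop study drug "return to the clinic for the Safety Follow-up Visit, which is required to be conducted within 40 days", then gives the tolerance and the early exit: "7 days] after the last dose of study drug or before the initiation of new anticancer therapy, whichever occurs first". Footnote c of Appendix 1 has the same form: "Safety Follow-up Visit: within 40 days [± 7 days] after last dose of study drug". The schedule table in Appendix 1 (repeated in SAP Appendix 1) is clearer: nominal day +40, window ±7.

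**Length of the safety window.** Protocol 9.5.1 says that all AEs and SAEs "will be reported until 40 days after last dose of study drug". Protocol 3.1 commits to monitoring over the same 40 days. The TEAE definitions in protocol 10.2.2 and SAP 6.6.2 also close at day 40, or at new anticancer therapy if that comes first. Table 5 adds death, withdrawal of consent and loss to follow-up as end points for recording.

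**Link between the two.** Protocol 10.1.5 treats the visit as the close of the window: concomitant medication is counted "up to 40 days after the patient's last dose (as of the Safety Follow-up Visit". That holds only if the visit is on or after day 40.

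**What follows the visit.** No later visit or call is scheduled. Under protocol 9.5.3 AEs are elicited by asking about the time since the previous visit. Under 7.6.2 one reason for leaving the study is "Completion of all study assessments".

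**The concern.** The window for counting events and the last contact at which patients are asked about them are set separately, and the contact may come first. A patient seen on day 33 is compliant with the schedule, yet no one is due to ask that patient about days 34 to 40.

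The effect has one direction. A visit on days 41 to 47 looks back over the whole window, and onsets after day 40 are not TEAEs. A visit on days 33 to 39 can only lose events. How much is lost depends on where in the window the visit happened to be booked.

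AE incidence is a primary endpoint and the safety set is about 8 patients, so one patient with or without a given event moves its incidence by 1/8 = 12.5 percentage points.

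The wording adds a smaller problem. A phrase that sets an upper limit (within 40 days) is joined to a two-sided tolerance, so sites must consult the table to learn what is meant.

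**Working it through.** **1. The plan's own total.** Protocol 3.1 gives about 35 weeks from Screening to Safety Follow-up. Its parts are screening 28 days = 4 weeks, treatment 25 weeks and post-infusion 6 weeks. 4 + 25 + 6 = 35 weeks. Reproduced.

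**2. Permitted visit days** (days after last dose; Appendix 1). Earliest 40 − 7 = 33; latest 40 + 7 = 47.

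**3. Days without a scheduled contact.** For a visit on day v, the gap is max(0, 40 − v).
- v = 33: 7 days; v = 39: 1 day; v = 40 to 47: 0 days.
- Largest share of the post-dose period: 7/40 = 17.5%.

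**4. An on-schedule five-cycle completer** (35-day cycles; last 13-cis-RA dose on Cycle 5 Day 25).
- Last dose: 4 × 35 + 25 = Day 165.
- Window closes: 165 + 40 = Day 205.
- Earliest visit: 165 + 33 = Day 198; latest: 165 + 47 = Day 212.
- Largest gap as a share of the TEAE window: 7/205 = 3.4%.
- The End-of-Treatment Visit does not help. The end of Cycle 5 is Day 175, so the visit falls on Days 168 to 182, which is 3 to 17 days after the last dose.

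**5. Antibody remaining at an early visit.** Fraction = 0.5^(24t/h), with t in days since the end of infusion and h the Cycle 1 half-life in hours from protocol 1.2.2 (median 186.52 in APN311-303; longest individual value 396.23 in APN311-202).

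| Last drug given | t at day 33 | h = 186.52 | h = 396.23 |
|---|---|---|---|
| Dinutuximab beta | 33 | 5.3% | 25.0% |
| 13-cis-RA (completer; infusion ends Day 11, so 14 days more) | 33 + 14 = 47 | 1.5% | 13.9% |

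**6. Illustration under assumed rates.** The documents give no rate for late-onset events. Assume that each of 8 patients has probability p of a new TEAE in the 40 days, that onset is uniform, and that all 8 are seen on day 33. Then q = p × 7/40, the expected number of patients with an onset in the gap is 8q, and the chance of at least one is 1 − (1 − q)^8.

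| p | q | 8q | At least one |
|---|---|---|---|
| 10% | 1.75% | 0.14 | 13% |
| 30% | 5.25% | 0.42 | 35% |
| 50% | 8.75% | 0.70 | 52% |

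These are upper-end figures for each p. Visits later than day 33 shrink the gap, and some of these events would be reported anyway.

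**7. Does a one-sided window fit?** With visits on days 40 to 47, the completer's participation runs from (28 + 205)/7 = 33.3 weeks to (28 + 212)/7 = 34.3 weeks, inside the stated 35. Day 212 is 212 − 175 = 37 days after the end of Cycle 5, inside the 6-week (42-day) post-infusion period.

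**The case against.** The strongest reply is that the duty to record events is set by date and not by visit. Protocol 9.5.1 and Table 5 require all AEs and SAEs to day 40, and the visit is not among the end points in Table 5. Related SAEs are reportable without time limit. Protocol 7.3 has AEs documented in all phases, 9.2.4 follows ongoing events to resolution or stabilisation, and 7.6.2 says only that patients may leave once assessments are complete. This stands, and it rules out the reading that days 34 to 40 go unobserved. What the duty does not supply is a contact: an investigator can report a new event only on learning of it, and the no-time-limit rule covers only related SAEs brought to the investigator's attention.

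A reader might also infer from the phrase within 40 days that no earliest day exists. The documents do not support that. The same sentence carries the ±7, footnote c repeats it, and the table fixes +40 ±7, so the earliest scheduled day is 33. The one earlier trigger is new anticancer therapy. Because the TEAE window closes when that therapy starts, it leaves at most the days between the visit and that start.

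The size is also fairly contested. The study is single-arm and descriptive, TEAEs are counted per patient with no person-time denominator, and day 40 is an upper limit for classifying events, so no treatment comparison is biased. Protocol 9.6 describes cytokine release, anaphylaxis and capillary leak as arising within minutes to hours of starting infusion, and little antibody remains by day 33 at the median half-life. Nothing in the documents suggests that new events cluster in days 34 to 40. All of this stands and keeps the point minor.

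**Conclusion.** The mismatch is real but small. A compliant visit on days 33 to 39 leaves 1 to 7 days of the TEAE window with no scheduled contact: at most 17.5% of the post-dose period and 3.4% of an on-schedule completer's 205-day window. Any error is towards missed non-serious or unrelated events. Visits on days 40 to 47 have no gap.

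The conclusion rests on reading 7.5.1 together with the Appendix 1 table, and on last dose meaning the later of the two study drugs, both of which SAP 6.3.1 counts as study drug. The completer figures assume no delays. The chance of 13% to 52% that at least one patient has an onset in the gap rests on assumed rates and should not be read as a forecast.

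Severity is minor. It is worth changing because the remedy costs almost nothing and AE incidence is a primary endpoint.

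**What to change.** - In protocol 7.5.1, Appendix 1 (window row and footnote c) and SAP Appendix 1, state the visit as 40 days (+7 days) after the last dose of study drug, counted from the later of the last dinutuximab beta and last 13-cis-RA dose. Naming the later dose matters because 7.6.1 lets one drug continue after the other stops. Text and table then agree, and the wording that mixes a limit with a tolerance goes.
- Keep the existing exception for new anticancer therapy.
- If a visit takes place before day 40 for any other reason, add a telephone check of AEs and concomitant medication on or after day 40.

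**Cost.** A few lines of text and less scheduling flexibility: the visit comes up to 7 days later than the earliest day now allowed, or one telephone call is added. The latest permitted day stays at 47 and the stated 35-week maximum is unchanged. The largest gap falls from 7 days to 0, apart from the new-therapy exception.

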7.5.2. Loss to Follow-up

If attempts to contact the patient by telephone are unsuccessful, additional attempts should be made to obtain protocol-required follow-up information: it may be possible to obtain the information from other contacts such as referring physicians or relatives. Attempts to establish contact should be documented in the patient's source documents. If a patient cannot be contacted despite all attempts, the patient will be considered lost to follow-up, and death information should be obtained through a public record search if local agencies permit.

7.6. Discontinuation From Study Treatment or From the Study

7.6.1. Patient Discontinuation From Study Treatment (End of Treatment for an Individual Patient)

Patients have the right to discontinue study drug at any time for any reason. In addition, the investigator has the right to discontinue a patient from study drug at any time. Patients who discontinue study drug for reasons other than relapse or progressive disease (PD) should be followed for assessments of preliminary anticancer activity (Section 8.4) and safety (Section 8.2), if possible.

The primary reason for discontinuation from study drug should be documented on the appropriate eCRF. Patients may discontinue study drug for reasons including but not limited to the following:

- Relapse
- PD
- AE
- Patient decision
- Pregnancy
- Any medical condition that the investigator or sponsor determines may jeopardize the patient's safety if he or she were to continue the study drug
- Use of any concurrent anticancer therapy, including chemotherapy, hormonal therapy, immunotherapy, standard or investigational agents (including Chinese [or other Country] herbal medicine and Chinese [or other Country] patent medicines) for the treatment of cancer [regardless of cancer type])
- Patient noncompliance
 - Study site staff should first counsel patients who are significantly noncompliant (eg, missing 2 treatment cycles) on the importance of study drug compliance and drug accountability. The investigator may, in consultation with the medical monitor, discontinue patients from treatment who are consistently noncompliant.

Treatment with dinutuximab beta should be permanently discontinued if the following toxicities occur:

• Grade 3 or 4 anaphylaxis

- Prolonged Grade 2 peripheral motor neuropathy
- Grade 3 peripheral neuropathy
- Grade 3 vision eye toxicity
- Grade 4 hyponatremia (< 120 mEq/L) despite appropriate fluid management
- Recurrent or Grade 4 capillary leak syndrome (requires ventilator support)

If dinutuximab beta or 13-cis-RA is discontinued permanently before cycle 5 for reasons other than relapse or PD, the other drug could be continued per the study protocol.

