5.4. Dose Delay or Modification

Dose modification

This protocol allows some alteration from the currently outlined infusion schedule of dinutuximab beta, but the maximum cumulative exposure will not exceed 100 mg/m²/cycle.

Based on the Investigator's evaluation of the severity of adverse drug reactions to dinutuximab beta, patients may undergo a dose reduction of 50% or a temporary interruption of the infusion. As a consequence, either the infusion period is prolonged or, if tolerated by the patient, the infusion rate may be increased up to 3 mL/h (continuous infusion), in order to administer the total dose.

Regarding the dose modification of 13-cis-RA, please refer to local label of 13-cis-retinoic acid.

Table 3: Recommended Dinutuximab Beta Dose Modification

Adverse reaction	Severity	Treatment modification
Any	Grade 1 or 2	Decrease infusion rate to 50%. After resolution, resume infusion at original rate.

Hypersensitivity reaction	eg, Hypotension	Interrupt infusion and administer supportive measures. After resolution, resume infusion at original rate.
Dilated pupils with sluggish light reflex ± photophobia		Interrupt infusion. After resolution, resume infusion at 50% rate.
Any	≥ Grade 3	Interrupt infusion and administer supportive measures. Resume infusion at 50% rate if adverse drug reaction (ADR) resolves or improves to Grade 1 or 2 within 3 days of onset. If 50% dose reduction is tolerated for ≥ 1 day, consider advancing infusion to full rate as tolerated. If toxicity (≥ Grade 3) recurs at 50% dose reduction, treatment should be discontinued. If toxicity (≥ Grade 3) recurs while at 100% infusion rate, stop infusion and reduce dose to 50% if toxicity resolves or improves to ≤ Grade 2 within 3 days of onset. Do not increase dose to 100% again.
Capillary leak syndrome		Interrupt infusion and administer supportive measures. Resume at 50% rate if ADR resolves or improves to Grade 1 or 2.
Capillary leak syndrome requiring ventilator support; allergic reaction (anaphylaxis), skin toxicity, severe neuropathic pain, any other Grade 4 toxicity (which does not recover to Grade 1 or 2 or baseline within 5 weeks)	Grade 4	Discontinue infusion. Contact sponsor to confirm if patient may continue infusion at the start of the subsequent cycle.

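### Section 7.6.1 permanently stops dinutuximab beta after Grade 4 capillary leak syndrome or anaphylaxis, but Table 3 leaves a restart at the next cycle to the sponsor, and no text says which rule governs

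*Protocol*

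**What the plan says.** Protocol Section 7.6.1 gives a list of toxicities under the instruction "Treatment with dinutuximab beta should be permanently discontinued if the following toxicities occur". Two of its entries are "Grade 3 or 4 anaphylaxis" and "Recurrent or Grade 4 capillary leak syndrome (requires ventilator support" (the entry closes its bracket there). The list also contains Grade 3 peripheral neuropathy, Grade 3 visual toxicity and refractory Grade 4 hyponatremia.

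Protocol Section 5.4, Table 3, has a Grade 4 row covering "Capillary leak syndrome requiring ventilator support; allergic reaction (anaphylaxis), skin toxicity, severe neuropathic pain, any other Grade 4 toxicity", the last item being qualified by failure to recover within 5 weeks. The action for that row is "Discontinue infusion. Contact sponsor to confirm if patient may continue infusion at the start of the subsequent cycle".

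Three other rows of Table 3 allow resumption:

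- Hypersensitivity reaction: "Interrupt infusion and administer supportive measures. After resolution, resume infusion at original rate".
- Any reaction of Grade 3 or higher: "Resume infusion at 50% rate if adverse drug reaction (ADR) resolves or improves to Grade 1 or 2 within 3 days of onset".
- Capillary leak syndrome: "Resume at 50% rate if ADR resolves or improves to Grade 1 or 2".

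Sections 3.1 and 7.3 refer the reader to Section 7.6 for further considerations on continuing or withdrawing treatment. Section 5.4 does not mention Section 7.6.1. The SAP contains no stopping rule.

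**The concern.** The same event has two different outcomes depending on which section the site opens. After ventilated CLS or Grade 4 anaphylaxis, Section 7.6.1 leaves nothing to decide. Table 3, the natural place to look while managing a reaction, tells the site to ask whether the patient may be infused again next cycle. It gives no criteria for the answer, and Section 11 sets up no study committee that could supply one.

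This is first a patient-safety matter. Neuroblastoma is mainly a paediatric disease, and both events are life-threatening. It also touches compliance. If 7.6.1 governs, a sponsor-confirmed restart is a protocol deviation, and Section 15.3 does not allow the investigator in China to deviate without ethics-committee and sponsor approval, unless China GCP provides otherwise.

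The analysis is affected only secondarily. The reading chosen decides whether the patient counts as permanently discontinued, which triggers the end-of-treatment visit (Section 7.4) and feeds the summary of events leading to discontinuation (Protocol 10.2.2, SAP 6.6.2). With 8 patients, reclassifying one moves that percentage by 1/8 = 12.5 points.

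**Working it through.** There is no sample size, power or error-rate figure to reproduce. The check is a comparison of the two rules, a search for a ranking, and a bound on the dose at issue.

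**Step 1. Events named in both places.**

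| Event | Section 7.6.1 | Table 3, Grade 4 row |
|---|---|---|
| Ventilated (Grade 4) CLS | Permanent stop | Stop infusion; sponsor may confirm the next cycle |
| Grade 4 anaphylaxis | Permanent stop | Stop infusion; sponsor may confirm the next cycle |

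Both places identify the CLS event by the need for ventilator support, so it is the same event. Firm conflicts: 2.

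**Step 2. Can the conflict be read away?**

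- *Within-cycle versus across-cycle scope.* The Grade 4 row itself addresses the following cycle, so it covers the same decision as 7.6.1.
- *The 5-week qualifier.* It most naturally belongs to the residual category of other Grade 4 toxicities. If it applied to the whole row, the row would still allow a restart for events that 7.6.1 ends.
- *Strength of wording.* Table 3 is titled as a recommendation, but 7.6.1 is also worded with should and not must. Neither wording sets a hierarchy.
- *Cross-references.* Sections 3.1 and 7.3 offer Section 7.6 as additional considerations. They do not say it overrides Table 3.
- *Section 9.6.* For severe infusion-related reactions it requires immediate discontinuation of therapy. That supports 7.6.1 but does not say the stop is permanent, and it mentions neither rule.

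**Step 3. Less direct tensions.** These can be resolved by letting the specific list prevail over the general rows, so they are secondary.

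- The row for any reaction of Grade 3 or higher makes no exception for Grade 3 anaphylaxis or Grade 3 peripheral neuropathy, both on the 7.6.1 list.
- The CLS resume row makes no exception for recurrent CLS. The general row does stop treatment if a toxicity of Grade 3 or higher recurs at the 50% rate. The severity cell of the CLS row is empty in the text available, and nothing here depends on it.
- Section 9.6 calls for interruption after Grade 3 vision toxicity, where 7.6.1 calls for a permanent stop.

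**Step 4. Bound on the dose at issue.** Inputs: 100 mg/m² per cycle and up to 5 cycles (Section 5.2.1).

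- Planned total = 5 × 100 = 500 mg/m².
- Floor = 0 mg/m², if the sponsor declines a restart.
- Ceiling after an event in Cycle k = (5 − k) × 100 mg/m², if the sponsor agrees and every later cycle is given in full.

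| Cycle of event | Ceiling (mg/m²) | Share of planned 500 |
|---|---|---|
| 1 | 400 | 80% |
| 2 | 300 | 60% |
| 3 | 200 | 40% |
| 4 | 100 | 20% |
| 5 | 0 | 0% |

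**Step 5. Frequency.** The documents give no Grade 4 rate for either event. Section 1.2.3 reports CLS at 40% in earlier experience, with no grade stated. Taken as any grade, 0.40 × 8 = 3.2 patients. That suggests only that the CLS instructions will probably be consulted. It is not a rate of Grade 4 CLS or of re-exposure, and it may be too high here because IL-2, itself a cause of CLS, is not given.

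**The case against.** The strongest reply is that both rules can be obeyed at once. Table 3 authorises no restart by itself: the site stops and calls, and the sponsor, bound by its own 7.6.1, says no. The pointers to Section 7.6 can be read as adding its rules on top of the dosing table, so that the stricter one controls. The Grade 4 row is also composite. Sponsor contact has a proper use for skin toxicity, severe neuropathic pain and other Grade 4 events outside the stop list, so the overlap may be loose drafting and not a policy of re-exposure. With about 8 patients at about 1 to 3 centres and a single sponsor, divergence is limited. The investigator may also stop drug at any time.

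Much of this stands as mitigation. It rules out automatic re-exposure and makes a careless restart unlikely. It does not remove the conflict. That the stricter rule wins is an inference no text states, and if the sponsor must always refuse, the instruction to ask is pointless for these two events.

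Two further objections are fair. The dose table counts remaining cycles and measures neither likelihood nor harm, and the 3.2-patient figure says nothing about Grade 4 events. The conclusion rests on neither. Interruption in Section 9.6 can also be read as a minimum first step, so the vision point is a matter of alignment only.

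**Conclusion.** The concern holds. The protocol is wrong as written: a rule in Table 3 conflicts with a safety stop rule in Section 7.6.1 for two named events, ventilated CLS and Grade 4 anaphylaxis, and no text in either document gives precedence. It should be fixed, and confidence is high because both rules are explicit.

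The practical size is bounded by the sponsor's answer: nothing if it declines, and up to 80% of the planned dose if it agrees after a Cycle 1 event and all four later cycles are given in full. How often the question will arise is unknown. The conclusion assumes only that the two sections describe the same events, which their matching descriptions support.

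**What to change.** 1. Add above Table 3 in Section 5.4: *The permanent-discontinuation list in Section 7.6.1 overrides every row of this table.*
2. Move ventilated CLS and Grade 3 or 4 anaphylaxis into a new Table 3 row whose only action is permanent discontinuation of dinutuximab beta, citing 7.6.1. The override sentence alone settles precedence. The new row makes the table safe to use on its own, because simply deleting the events from the Grade 4 row would drop them into rows that permit resumption.
3. Limit the CLS resume row to a first episode below Grade 4. Keep sponsor contact for the Grade 4 events that are not on the 7.6.1 list.
4. Align the Section 9.6 sentence on Grade 3 vision toxicity with 7.6.1.

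If the sponsor does intend re-treatment after any of these events, amend 7.6.1 for that event instead, so that each event has one action.

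The cost is one added sentence, one new and two edited table rows, and one edited sentence in Section 9.6. Under Section 14.2.1 this is an amendment needing authority and ethics-committee review before use, unless the sponsor treats it as removing an immediate hazard. No patients or procedures are added. The downside is the review time, and the loss of sponsor-approved re-treatment for any patient who would have been restarted under Table 3. The documents do not allow that number to be estimated.

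### Section 7.6.1 permanently stops dinutuximab beta after severe anaphylaxis and after recurrent or ventilator-requiring capillary leak syndrome, but Table 3 leaves a restart open for these named events and no sentence says which rule governs

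*Protocol*

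**What the plan says.** Protocol Section 7.6.1 sets the permanent-stop rule: "Treatment with dinutuximab beta should be permanently discontinued if the following toxicities occur". Six toxicities follow. They include "Grade 3 or 4 anaphylaxis", "Recurrent or Grade 4 capillary leak syndrome (requires ventilator support" (with a closing bracket in the original) and "Grade 3 vision eye toxicity". The others are prolonged Grade 2 motor neuropathy, Grade 3 peripheral neuropathy, and Grade 4 hyponatremia despite fluid management. The section provides no restart for any of them.

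Protocol Section 5.4, Table 3, gives recommended dose modifications. Three rows matter:

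- **Grade 4 row.** It covers "Capillary leak syndrome requiring ventilator support; allergic reaction (anaphylaxis), skin toxicity, severe neuropathic pain, any other Grade 4 toxicity", the last of these qualified by non-recovery within 5 weeks. The infusion is stopped, and then: "Contact sponsor to confirm if patient may continue infusion at the start of the subsequent cycle".
- **Capillary leak row.** Interrupt, give support, then: "Resume at 50% rate if ADR resolves or improves to Grade 1 or 2".
- **General row for any reaction of Grade 3 or worse.** "Resume infusion at 50% rate if adverse drug reaction (ADR) resolves or improves to Grade 1 or 2 within 3 days of onset". If toxicity of that grade returns at the 50% rate, treatment stops. If it returns at full rate and improves within 3 days, the patient goes back to 50%.

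Section 9.6 requires immediate discontinuation of therapy for a severe infusion-related reaction, without saying that this is permanent. It says that treatment must be interrupted for Grade 3 vision toxicity. Sections 3.1 and 7.3 refer the reader to Section 7.6 on continuing and withdrawing treatment. The SAP has no rule on the matter.

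**The concern.** A permanent stop and a possible restart cannot both apply to the same event in the same patient. Table 3 is the dosing table that an investigator is likely to consult while an infusion is running. It does not mention Section 7.6.1, so someone who follows the table alone could re-expose a patient, typically a child, to a drug that another section has ended for that patient.

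There is a smaller reporting side. A permanent stop triggers the End-of-Treatment visit within 7 days (Section 7.4), and SAP Section 6.6.2 counts events leading to discontinuation separately from those leading to interruption. With 8 patients, moving one patient between categories shifts a percentage by 1/8 = 12.5 points.

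**Working it through.** The plan states no figure here, so the check sets the rules side by side, event by event.

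**Named events in the Grade 4 row**

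- Grade 4 anaphylaxis: Section 7.6.1 stops permanently; Table 3 stops the infusion but allows the next cycle if the sponsor confirms. Conflict.
- Ventilator-requiring capillary leak syndrome: the same two instructions. Conflict.
- The 5-week qualifier reads as belonging to the other Grade 4 toxicities. If it applied to the whole row, the sponsor-confirmed restart would still be there.

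**Recurrent capillary leak syndrome**

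- Grade 3 or worse, recurring at the 50% rate: Section 7.6.1 stops, and so does Table 3 through its general row. Agreement.
- Grade 3 or worse, recurring at full rate: Section 7.6.1 stops; the general row allows a return to 50%. Conflict.
- Lower-grade recurrence: the capillary leak row allows 50% on improvement and is not limited to a first episode. This conflicts if *recurrent* in Section 7.6.1 means any grade.
- If the ventilator bracket also qualifies *recurrent*, only ventilated recurrences fall under Section 7.6.1, and they belong to the Grade 4 row. The conflict then reduces to that row. On that reading *recurrent* would add nothing to the Grade 4 criterion, which favours the wider reading, but the text does not settle it.
- The severity cell of the capillary leak row is empty in the text available for review. If it should read Grade 3 or worse, recurrence at full rate would still conflict on the wider reading.

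**Events reached only through the general row (secondary)**

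- Grade 3 anaphylaxis: the row states no exception, but Section 9.6 requires immediate discontinuation of therapy for severe infusion-related reactions.
- Grade 3 peripheral neuropathy: no exception stated. Section 9.6 allows interrupt-and-resume only for Grade 2 and permanently stops prolonged weakness, so it leans towards Section 7.6.1.
- Grade 3 vision toxicity: no exception stated, and Section 9.6 speaks of interruption.

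The remaining two listed toxicities are not relied on. Section 9.6 supports the permanent stop for prolonged weakness, and Table 3 does not name hyponatremia.

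**Precedence.** The pointers in Sections 3.1 and 7.3 are the nearest thing to a ranking. They send the reader to Section 7.6 without placing it above Table 3.

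**Count.** Of 6 listed toxicities, Table 3 names 2 and leaves a restart path for them. The general row reaches 2 more, on weaker ground.

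**How often the capillary leak row may be used.** Section 1.2.3 gives capillary leak syndrome of any grade at 40%. With 8 independent patients, the expected number is 8 × 0.40 = 3.2, and the chance of at least one is 1 − 0.60^8 = 0.983. The 40% may be too high here, because the same section links the syndrome to IL-2, which this study omits. These figures describe first occurrence at any grade, not the conflict.

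**The case against.** The strongest reply is that the two texts do different jobs. Table 3 is headed as a recommendation and guides infusion-rate handling; Section 7.6.1 concerns the end of treatment and names specific toxicities at specific grades. A specific permanent-stop list would ordinarily displace a row for any reaction, and Sections 3.1 and 7.3 direct the reader to Section 7.6 on just this question. That is a sensible inference, and it is why the general-row point is only secondary. It does not clear up the Grade 4 row, which itself names the two events. Section 7.6.1 also uses *should*, so the difference in force is not obvious.

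Second, the Grade 4 row is a gate, not a permission. It also covers events outside the permanent-stop list, and a sponsor applying Section 7.6.1 would refuse a restart after anaphylaxis or ventilated capillary leak. This stands as a real safeguard. The half-rate restart in the capillary leak row has no such step.

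Third, Table 3 does limit recurrence in part, and Section 9.6 does bear on anaphylaxis. Both stand. A reader might infer that Grade 3 anaphylaxis may simply be restarted at 50%, or that no second capillary leak episode ever stops treatment. The documents support neither.

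Fourth, interruption in Section 9.6 can describe the immediate action for vision toxicity, with Section 7.6.1 giving the final disposition. That is a fair reading; the wording is still worth aligning.

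**Conclusion.** The contradiction holds for the named events. It is firmest for Grade 4 anaphylaxis and ventilator-requiring capillary leak syndrome. It also holds for recurrent capillary leak syndrome, outside the case where both rules stop treatment, provided that *recurrent* is not confined to ventilated episodes. Three general-row gaps (Grade 3 anaphylaxis, neuropathy and vision toxicity) are lesser drafting faults.

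A reader might go further and count four of the six toxicities as restartable on equal terms. The text does not support that: two are named, and two are reached only by a general row that the specific list may displace. Nor can a probability of meeting the recurrence conflict be given, since the documents report no recurrence rate; they also give no rate for Grade 3 or 4 anaphylaxis or for ventilated capillary leak syndrome. Re-exposure, different handling between sites and shifted discontinuation counts are possible consequences, not demonstrated ones. Section 7.6.1 also lets the investigator stop treatment at any time.

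This is a wording fault with a bearing on patient safety. It does not threaten the planned analyses, but it is worth correcting because the correction is so cheap.

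**What to change.** 1. In Section 5.4, at Table 3, state that the permanent-discontinuation toxicities in Section 7.6.1 override every row of the table.
2. Take anaphylaxis and ventilator-requiring capillary leak syndrome out of the next-cycle option in the Grade 4 row. The option can stay for the row's other events.
3. Limit the half-rate restart in the capillary leak row to a first episode that does not need ventilator support.
4. In Section 9.6, bring the Grade 3 vision toxicity wording into line with the permanent stop in Section 7.6.1.

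The first change also closes the general-row gaps, and the third settles what recurrence means in practice. The cost is protocol wording only, through the amendment route in Section 14.2.1. No extra data, visits or patients are needed.
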